**6. Institutional Review Board – Ethics Committee:**

CEIm del Hospital Universitario de Salamanca

**7. Monitor:** [name] (IECSCYL-IBSAL)

**8. Experimental Product:** Hemopatch®

Pharmaceutical form: Collagen patch derived from bovine skin, coated with NHS-PEG (pentaerythritol polyethylene glycol ether tetrasuccinimidyl glutarate).

**9. Clinical trial phase:** Phase III.

**10. Main Objective:** To analyze the efficacy of the application of Hemopatch® directly on the pulmonary suture line as prevention of postoperative

air leak in patients at high risk after pulmonary resection. Decrease in the postoperative air leak rate (air outflow through the drains on the 5th postoperative day).

**11. Secondary objectives:** To analyze the effectiveness of the procedure measured in terms of:

-Clinical

- o Duration of postoperative air leakage
- o Rate of reinsertion of pleural drainage for symptomatic pneumothorax
- o 30-day postoperative readmission rate for recurrence of symptomatic pneumothorax.
- o Cardiorespiratory related complications.

-Radiologicals:

- o Presence of pneumothorax on chest radiograph.

**12. Design:** Prospective, multicenter, open-label, randomized.

The study is divided into two phases:

1st- Treatment: intra-operative application of the Hemopatch® patch.

2º- Postoperative follow-up: Daily until drainage removal or hospital discharge, and at 30-90 days postoperatively.

**13. Study disease:** Prolonged postoperative air leak in patients at risk.

**14. Study population:** Patients who are to undergo scheduled anatomic pulmonary resection (excluding pneumonectomy) and D classified, according to the postoperative prolonged air leak risk scale (index > 1.5) (Patient age over 65 years (1 point), body mass index BMI<25 kg/m^2 (2 points), FEV1<80% (1.5 points) and presence of pleural adhesions during surgery (1 point). Air leak risk scale. A total of 276 patients were included, 138 in the experimental group and 138 in the control group.

**15. Study duration:** From the inclusion of the first patient to the end of follow-up 18 months. Recruitment period: 18 months from the inclusion of the first patient in the study.

## 2. ABBREVIATIONS

AA: Adverse events

AAG: Serious Adverse Event

AEMPS: Agencia Española del Medicamento y Productos Sanitarios

ARCO: Association Research Circulation Osseus

GCP: Good Clinical Practice

CEIm: Committee on the Ethics of Research on Medicinal Products.

CRD: Data Collection Notebook

CRO: Clinical Research Organization

PAL: Prolonged Air Leakage

FEV1: First-second exhaled volume

GMP: Good Manufacturing Practice

HUS: University Hospital of Salamanca

ICH: International Conference on Harmonization

IP: Principal Investigator

LPDP: Personal Data Protection Act

WHO: World Health Organization

SOP: Standard Operating Procedure

RNP: Patient-reported records

CT: Computerized axial tomography

WMA: World Medical Association

### **3. GENERAL INFORMATION:**

#### **3.1. Clinical trial Identification:**

Code: HEMOPATCH/FAP/2014

Title: "Prospective, Multicenter, Open-Label, Randomized, Phase III Clinical Trial of Prevention of Prolonged Air Leak After Lung Resection in High-risk Patients, Applying HEMOPATCH®"

#### **3.2. Clinical trial:**

Phase III

#### **3.3. Investigational product:**

- HEMOPATCH®
- Nature of investigational product: Patch
- Qualitative composition: Collagen patch derived from bovine skin, coated with NHS-PEG (pentaerythritol polyethylene glycol ether tetrasuccinimidyl glutarate).
- Product dosage: 3 units/patient of 4.5x9 cm

#### **3.5. Promotor:** Fundación Instituto de Estudios Ciencias de la Salud de Castilla y León (IECSCYL)-Instituto de Investigación Biomédica de Salamanca (IBSAL)

#### **3.6. Responsible for investigational product:** BAXTER

**3.7. Study duration:** From the inclusion of the first patient to the end of follow-up 18 months. Recruitment period: 18 months from the inclusion of the first patient in the study.

## 4. RATIONAL BASIS FOR THE TRIAL, JUSTIFICATION AND OBJECTIVES

### INTRODUCTION

#### **Definition, epidemiology and clinical features of postoperative prolonged air leakage**

Postoperative prolonged air leak (PAFL) is the outflow of air through the pleural drains after surgery for a prolonged period of time. It is the most frequent technical complication of lung resection (Rice TW, 2002) and, in addition to being a risk for the patient's health (Brunelli A, 2006; Varela G, 2004), it represents a considerable expense for the health system (Varela, G, 2005). An overall incidence has been described in patients with pulmonary lobectomy between 10 and 15% (Cerfolio RJ, 2002; Brunelli A, 2004). Patients with this complication must have an intrapleural drainage for a longer time, which increases pain, anxiety and stress, as well as increasing the risk of other cardiorespiratory complications (Cerfolio RJ, 2002 Okereke I, 2005). On the other hand, it has been demonstrated that this complication is a determining cause of increased hospital stay (Brunelli A, 2006; Varela G, 2004; Bardell T, 2003; Irshad K, 2002).

#### **Current treatments for prolonged postoperative air leak.**

Various prophylactic measures have been attempted to prevent the complication. Such measures include both surgical techniques such as the "pleural tent" (Brunelli A, 2002) and the use of lung suture supports (Miller JI Jr, 2001) or the use of surgical adhesives (Wain JC, 2001; Fabian T, 2003; Allen MS, 2004). Regarding the latter, there is some controversy in the literature since, in the face of randomized clinical trials demonstrating their effectiveness (Wain JC, 2001; Fabian T, 2003; Allen MS, 2004), a meta-analysis has been published (Belda-Sanchís J, 2010) that advises against their routine use due to two problems: the lack of conclusive demonstration of the effect and the high cost of the products. Modifications to the usual surgical techniques have also been suggested, such as the "Fissure-less technique" (Al Refai M, 2010). The selection of higher risk patients according to a risk scale may justify the routine use of prevention methods.

The base of Hemopatch® is polyethylene glycol, a product that has been widely used in the treatment of air leakage, in fact there are ongoing Phase IV studies (NCT01394978 and NCT01867658), on a collagen base that facilitates the action of the product. The safety of the Hemopatch® product has been demonstrated in multiple studies (Fingerhut 2014, Lewis KM 2014). Hemopatch® is CE marked and is a product that is being used in most hospitals.

We have studies on the use of Hemopatch® for air leak (Lewis KM 2014),

Phase III studies have been conducted with similar collagen patches (NCT00293514) for the treatment of air leak which are the basis for further studies such as the one designed by the investigators.

## JUSTIFICATION

Therefore, they justify the performance of this clinical trial:

- The existence of a frequent clinical problem such as prolonged postoperative air leak with no solution so far.
- It is a pathology that causes pain, anxiety, stress, in addition to increasing the risk of other cardiorespiratory complications.
- We can identify the population most at risk of developing this complication.

With this background, we set ourselves the objective of developing a therapeutic alternative in patients at risk of prolonged postoperative air leak based on the topical application of a Hemopatch® collagen patch.)

## OBJETIVES

### Main objective:

To analyze the efficacy of the application of Hemopatch® directly on the pulmonary suture line as prevention of postoperative air leak in patients at high risk after pulmonary resection. Decrease in the postoperative air leak rate (air outflow through the drains on the 5th postoperative day).

### Secondary objectives:

To analyze the efficacy of the procedure measured in terms of:

-Clinical:

oDuration of postoperative air leak.

oRate of reinsertion of pleural drainage for symptomatic pneumothorax

o 30-day postoperative readmission rate for recurrence of symptomatic pneumothorax. oRelated cardiorespiratory complications.

-Radiologicals:

oPresence of pneumothorax on chest radiograph.

## 5. CLINICAL TRIAL CLASS AND DESIGN

### 5.1. PHASE

Prospective, multicenter, open-label, randomized, phase III clinical trial of prevention of postoperative air leak after pulmonary resection in high-risk patients by application of HEMOPATCH® directly to the pulmonary suture line.

### 5.2. GLOBAL DESIGN

#### 5.2.1. DESIGN

Prospective, multicenter, open-label, randomized, prospective study with a control group and an experimental treatment group.

#### **5.2.3. Expected duration of participation of the participants. Trial sequence and periods.**

The patient inclusion period is 18 months. The follow-up of the patients will be from 1 to 3 months and will be carried out in several visits according to the proposed scheme (see Annex I), therefore the patients will be evaluated longitudinally for all clinical and paraclinical parameters. The study ends with the last follow-up visit of the last patient treated, between 1 and 3 months after the intervention.

### **5.3. PRE-INCLUSION, TREATMENT AND FOLLOW-UP PERIODS**

- A.** Patients will be provided with a detailed explanation of the technique and its advantages and disadvantages (technical problems and possible complications). They will be provided with the Study Information and Informed Consent Form to sign and date if they agree to participate in the study (Annex VI).
- B.** Participating hospitals have been selected by surgical volume of at least 100 major resections (lobectomy and anatomic segmentectomy) per year, plus at least 100 atypical resections.
- C.** Randomization will be carried out according to the order of inclusion against a table of random numbers generated in Excel, this task will be performed by the data manager.

#### ***Baseline. Pre-treatment evaluation.***

*Patients who meet the inclusion criteria will be evaluated by the usual preoperative study.*

#### ***Treatment.***

*The experimental group will be administered up to 6 Hemopatch® patches applied at the end of the pulmonary resection on the suture lines of the pulmonary parenchyma, once the absence of air leak or minimum grade 1 according to the Machiarini scale (Annex III) has been verified.*

### **Perioperative Protocol.**

They will be admitted to hospital the day before surgery and will receive standardized postoperative care; this care includes extubation of the patient in the operating room at the end of the operation, postoperative analgesia according to the protocol of each center, and the usual respiratory care. The type of surgical approach will not be standardized and will be at the discretion of the surgeon, who in all cases will be an investigator of this project. The suture of the pulmonary parenchyma will be performed with mechanical staplers or resorbable manual suture material; in no case will adhesives or prosthetic material for reinforcement other than that contained in the Investigational Product be added for the experimental group. The use of surgical adhesives (Tachosil® or Hemopatch® itself) is also excluded in the control group, since the intervention under study will be used in the experimental group.

The pleural space will be drained with one or two 24-28 French caliber multifenestrator tubes. Once the intervention has been completed, the drainage tube or tubes will be connected to a bottle with a valve system connected or not to aspiration according to the uses of each center.

### **FOLLOW-UP AND EVALUATIONS**

The follow-up will be done daily during the time the patient is admitted. A daily visit will be made until the patient is discharged from the hospital.:

#### ***Clinical parameters***

- o Assessment of the existence of air leakage.
- o Amount of air leak.
- o Existence of cardiorespiratory complications.
- o Need for placement of pleural drainage due to symptomatic pneumothorax.

#### ***Radiological parameters***

- o Presence of pneumothorax in the chest X-ray.

The duration of admission will depend on the clinical evolution. This will take into account:

Clinical parameters:

- The patient is capable of self-care
- Afebrile
- Does not require opioids for pain control.

- Absence of significant effusion or pneumothorax

Analytical parameters:

- Normal blood count, coagulation and biochemistry.

Subsequent follow-up will be carried out in consultation within 1-3 months post-operatively, collecting the following evolutionary data:

- Evaluate the clinical evolution especially related to the appearance of complications.
- Data collection: special attention to the clinical situation of the patient.
- Radiological parameters: chest X-ray, BP and L projections.

The trial sponsor will provide all patients included in the study with a follow-up card identifying that these patients have been treated with Hemopatch® patches.

## 6. PARTICIPANT SELECTION

### 6.1. TARGET POPULATION

The population will consist of patients undergoing scheduled anatomic lung resection (excluding pneumonectomy) and classified D, according to the postoperative prolonged air leak risk scale (index > 1.5) ( Patient age over 65 years (1 point), BMI body mass index<25 kg/m^2 (2 points), FEV1<80% (1.5 points) and presence of pleural adhesions during surgery (1 point)).

### 6.2. INCLUSION CRITERIA

- Age between 18 and 80 years
- Patients who are going to undergo scheduled anatomical lung resection (excluding pneumonectomy).
- Patients class D on the air leak risk scale.

Patients included in the study must meet all inclusion criteria.

### 6.3. EXCLUSION CRITERIA

Patients who present any of the following exclusion criteria cannot be included in the clinical trial:

- Those who in the judgment of the investigator are not in an adequate situation to tolerate the procedure.
- Clinical and anesthetic criteria that contraindicate surgery (e.g. ASA IV-V).
- Severe uncontrolled disease
- Pregnant women
- Individuals who are taking a clinical research drug or have participated in a clinical research study (with an authorized or unauthorized product) in the 30 days prior to randomization.
- Lack of informed consent or revocation of consent.
- Postoperative mechanical ventilation or thoracic surgical reintervention in the month of follow-up.

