#### 8.2. CLINICAL TRIAL DEVELOPMENT

The Hemopatch product administration procedure (day 0 of the study) and the rest of the study visits and procedures will take place in each of the participating hospitals.

**-Visit 1: Selection:** The selection of candidate patients will be made by the Thoracic Surgery Department of each participating hospital. During this visit, and once the usual evaluation has been carried out, in response to the demand for care for which he/she attends, the patient potentially suitable for the study will be informed of the objectives of the study and the overall requirements. Informed consent will be obtained prior to any study-specific assessment. The patient will then undergo a clinical evaluation to ensure compliance with the inclusion and exclusion criteria.

The patient's medical record should record how the patient agrees to participate in the HEMOPATCH/FAP/2014 clinical trial, date of consent signature, assigned patient

number and study sponsor.

The date of the visit shall be recorded and collected:

- Presentation of written informed consent.
- Medical history, including concomitant diseases and medication, supportive treatment and baseline medical conditions.
- Complete physical examination.
- Serum pregnancy test in fertile women.
- Respiratory functional evaluation
- Chest CT scan.

Once the results of all the above-mentioned procedures have been obtained, and it has been verified that all the inclusion criteria have been met and none of the exclusion criteria have been met, the patient may continue in the study and be randomized. If, on the other hand, the patient does not meet the inclusion criteria, he/she will not be able to continue in the study and the reason for the patient's non-selection must be recorded in the CRD.

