## 12. STATISTICAL ANALYSIS

The data collection notebooks will be processed by a pre-set and validated Clinical Data Computer System. After double data recording, resolution of all inconsistencies and coding using the medical dictionaries, a final quality control process will be applied and in case of compliance the database will be considered free of errors and will proceed to freeze and perform the statistical exploitation of the data. The results of the clinical trial will be analyzed in the intention-to-treat population.

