### 12.1. Population for analysis

The efficacy and safety analysis will include all patients enrolled in the study. Efficacy analyses will be performed on data from the intention-to-treat population.

The term "treatment period" used for efficacy and safety analyses refers to the period from cell administration and the end-of-treatment week (+/-7 days). This period will form the basis for the efficacy and safety summaries.

The primary efficacy data set will consist of all patients in the study who have completed all treatment. Events occurring in patients who have been withdrawn early will also be included if the patients meet the withdrawal criteria.

For the primary endpoints, an analysis will be conducted using the evaluable patient data set as well as the primary efficacy data set. Summaries of the safety data will include all patients treated in the study. The primary and secondary data set will be defined in a statistical analysis plan.

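### Section 6.3 excludes patients for events that can only occur after randomisation, which conflicts with the intention-to-treat statements, and section 12.1 does not resolve the conflict

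*Combined protocol and SAP*

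**What the plan says.** Section 6.3 opens with "Patients who present any of the following exclusion criteria cannot be included in the clinical trial". Its last item is "Postoperative mechanical ventilation or thoracic surgical reintervention in the month of follow-up", and the item before it is "Lack of informed consent or revocation of consent".

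Section 8.2 puts the eligibility check at Visit 1: once all inclusion criteria are met and "none of the exclusion criteria have been met, the patient may continue in the study and be randomized". Product administration is Visit 2. The primary outcome is air outflow through the drains on postoperative day 5 (section 4, main objective), and the trial is open-label (section 5.2.1).

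On the analysis population, section 12 states: "The results of the clinical trial will be analyzed in the intention-to-treat population". Section 12.1 says "The efficacy and safety analysis will include all patients enrolled in the study" and "Efficacy analyses will be performed on data from the intention-to-treat population". The same section then says "The primary efficacy data set will consist of all patients in the study who have completed all treatment". It counts events in early withdrawals only when the withdrawal criteria are met, mentions an evaluable set without defining it, and leaves the data sets to a statistical analysis plan. The text supplied contains no such definitions.

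Section 6.4 names neither ventilation nor reintervention as a reason to leave the trial. It does list withdrawal of consent. It also notes that a single dose is given and recommends that patients stay in the study after receiving it.

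**The concern.** An exclusion criterion should be decidable before randomisation. This one depends on what happens in the month after surgery. Its window opens after allocation and closes well after day 5, so it could be invoked when both the arm and the primary outcome are known. Reintervention also involves a surgeon's decision, and in this trial every operating surgeon is an investigator who knows the assignment.

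What is at stake is the randomised comparison. If patients are removed under this item, if removal differs between arms and if it is related to leak, the day-5 comparison is conditioned on a post-randomisation event and is biased. As the plan stands, two analysts could each follow the document and report different primary populations.

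**Working it through.** **1. Order of events.** Section 8.2 runs: consent, eligibility check, randomisation, then product administration at Visit 2. The events in the 6.3 item come after surgery. One eligibility component, pleural adhesions, is scored during surgery, so randomisation might in practice take place in theatre. The events would still follow it. No reading makes this a baseline criterion.

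**2. The rules side by side, for a randomised patient who is ventilated or reoperated on within the month.**

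| Rule | Consequence |
|---|---|
| 6.3 | Cannot be in the trial |
| 12 and 12.1, intention-to-treat | In the efficacy analysis, assigned arm |
| 12.1, all enrolled | In |
| 12.1, completer set called primary | Probably in, since the single dose is given during surgery, but the term is not defined |
| 12.1, early withdrawals | In only if a 6.4 criterion applies; items such as compromised health, a serious adverse event or a serious protocol violation leave that to the investigator |
| 12.1, evaluable set | Undefined |

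Section 12.1 does not say which rule prevails.

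**3. The plan's own figure.** Inputs from section 5.2.2 are 27% against 13.5%, two-sided alpha 0.05, power 0.80 (the stated beta of 0.80, read as power) and 1:1 allocation. With pooled variance under the null and no continuity correction, mean rate 0.2025:

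n per arm = [1.96·√(2·0.2025·0.7975) + 0.8416·√(0.27·0.73 + 0.135·0.865)]² / 0.135² = (1.114 + 0.472)² / 0.018225 ≈ 137.9, so 138 per arm and 276 in total. This matches the plan. It contains no allowance for removed patients. Keeping everyone leaves power at 0.80. Removing 5% of each arm at random gives 0.78, so loss of power is the smaller issue.

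**4. Size of the selection effect (assumed inputs).** Let r be the share of an arm excluded, q the leak rate among those excluded, and p the true rate in the whole arm. The rate among those kept is

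(p − r·q) / (1 − r), with n = 138·(1 − r), rounded.

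Take no true effect (p = 0.27 in both arms), with 1% of controls and 3% of experimental patients excluded and q = 1:

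- Control: (0.27 − 0.01)/0.99 = 0.2626, n = 137
- Experimental: (0.27 − 0.03)/0.97 = 0.2474, n = 134
- Apparent risk ratio: 0.2474/0.2626 = 0.942

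The chance of a significant result favouring the patch comes from full binomial enumeration of the two-sided pooled chi-square test at 0.05, without continuity correction. With no exclusion it is 0.0250, and power under the planned rates is 0.804.

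| Excluded, control / experimental | q = 27% | q = 50% | q = 100% | Risk ratio at q = 100% |
|---|---|---|---|---|
| 1% / 2% | 2.5% | 2.8% | 3.5% | 0.971 |
| 1% / 3% | 2.5% | 3.1% | 4.8% | 0.942 |
| 3% / 3% | 2.5% | 2.5% | 2.5% | 1.000 |
| 6% / 3% | 2.5% | 1.8% | 0.8% | 1.108 |

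The null comparison is therefore undisturbed when exclusion is equal with equal q, or when exclusion is unrelated to leak (q = 27%). Otherwise the shift can go either way.

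**The case against.** The best defence is that the analysis section points towards keeping these patients. It says intention-to-treat twice and all enrolled once, section 6.4 recommends continuation after the dose, and no passage orders anyone's removal from the analysis. That much stands, and it rules out some stronger readings. A reader might infer that the trial plans to drop these patients, or that the completer set drops them. Neither follows: a strict intention-to-treat reading keeps them, and a patient who received the single intraoperative dose can be said to have completed treatment. A reader might also infer that safety data would be lost, but sections 12.1 and 12.4 can be read as keeping all treated patients.

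The second objection is that every rate in the illustration is assumed. That also stands. Moreover, with no effect on leak, unequal exclusion needs a cause of its own, such as discretionary reintervention under open label or an effect of the patch on these events. The documents establish neither, so they do not support saying that the bias favours the patch, or that it is large.

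What the defence does not do is reconcile the text. The intention-to-treat wording shares a section with a differently worded primary set, an undefined evaluable set and a deferral, while 6.3 says without qualification that these patients cannot be in the trial.

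**Conclusion.** The point holds as a contradiction about who is in the primary analysis. It does not show that patients will be excluded or that the result will be biased. The item in 6.3 cannot act before randomisation, and applying it as written would breach the intention-to-treat and all-enrolled statements.

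If it were applied unequally and in relation to leak, modest imbalances of 1% against 2–3% would move a nominal 2.5% false-win chance to between 2.8% and 4.8%, and the reverse imbalance of 6% against 3% would lower it to 1.8–0.8%. These figures assume a 27% leak rate in both arms and 50–100% leak among those excluded; the exclusion shares are also assumptions. The need to correct the text does not depend on them. It rests on the primary population being open to choice after the outcome is known.

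**What to change.** - **Section 6.3:** delete the ventilation and reintervention item. Keep lack of consent here, and handle revocation after randomisation only under 6.4, which already lists it.
- **Section 12.1:** state that the primary efficacy set is all randomised patients in their assigned arm. Remove the condition that early withdrawals must meet the withdrawal criteria. Define any completer or evaluable set and label its analysis supportive.
- **Reporting:** give postoperative ventilation and thoracic reintervention by arm as outcomes. Show an analysis without these patients only as a labelled sensitivity analysis.
- **Secondary, for the analysis plan:** say how a randomised patient with no assessable day-5 leak status is counted. One option is to count such patients as leaks in both arms, with best-case and worst-case sensitivity analyses. Reconcile the rule with the bar on imputation in section 12.2. This gap exists independently of the 6.3 item.

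The cost is a short amendment to 6.3, 12.1 and 12.2 plus wording in the analysis plan, with no extra patients or visits; 138 per arm is preserved. The downside is that some ventilated or reoperated patients will add noise to the day-5 assessment.
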